6. MODIFICATIONS

6.1. Modifications from the Approved Clinical Study Protocol

Protocol Amendment 3 (Version 4.0 dated 07-Oct-2022) permitted alcohol consumption with restrictions on amount and timing with respect to scheduled study visits. The summarization and main analysis of the primary endpoint will be repeated for categories of whether alcohol historically helped tremor (see Section 8.3.3.4).

Protocol Amendment 4 (Version 5.0 dated 10-Jan-2023) included an update to eligibility criteria and statistical analyses to include participants who are receiving propranolol for the treatment of essential tremor.

- Objectives and endpoints were updated to include the monotherapy cohort (SAGE-324), adjunct therapy cohort (SAGE-324 + propranolol), and overall population.
- Sample size and power were updated to focus on required enrollment for monotherapy participants; the adjunct therapy cohort was not based on statistical significance, but clinical considerations.
- Randomization was stratified by baseline propranolol use.
- Summarization and analysis of the primary efficacy variable, secondary efficacy variables was updated to be performed for the monotherapy cohort (primary cohort), adjunct therapy cohort (for directional investigation, excluding MCP-Mod analysis), and overall.

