8.2.3. Demographics and Baseline Characteristics

Demographic data (age, sex, race, and ethnicity) and baseline characteristics (height, weight, BMI, dominant upper limb) will be summarized with descriptive statistics by treatment group using the Safety Analysis Set. This summarization will be done by stratum (monotherapy cohort and adjunct therapy cohort) and overall.

Baseline subgroups will be summarized for the following categories:

- Race (Black or African American, White, Asian, Other)
- Sex (Female, Male)
- Age (<65, 65 to 80 years)
- BMI (<18.5, 18.5 to <25, 25 to <30, ≥30 kg/m²)

Listings will be provided for demographics, other baseline characteristics, and informed consent data.

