8.3.3.4. Subgroup Analyses of Primary Endpoint

The descriptive summarization and MMRM analysis of the primary endpoint will also be presented by the following subgroups:

• Age group: <65 years, 65 to 80 years

Statistical Analysis Plan Methods Version 1.0 17-Jun-2024 Protocol Number: 324-ETD-202 (Version 6.0 2 November 2023)

- Sex: Male, Female
- Race: White, Black or African American, Asian, Other
- BMI: $<18.5 \text{ kg/m}^2$, 18.5 to $<25 \text{ kg/m}^2$, 25 to $<30 \text{ kg/m}^2$, $\ge 30 \text{ kg/m}^2$
- Age at ET diagnoses: <40 years, 40 to 60 years, >60 years
- Age participant thinks ET started: <20 years, 20 to <40 years, 40 to 60 years, >60 years
- Years with ET diagnosis: <6 years, 6 to 10 years, and >10 years
- Years since participant thinks ET started: <6 years, 6 to 10 years, and >10 years
- Alcohol helps tremor: Yes (Intermediate, Worked Well), No (No, a little), NA
- Baseline TETRAS performance subscale part 4 upper limb tremor score on the dominant side: <7.5 and >7.5
- Baseline TETRAS performance subscale part 4 upper limb tremor score on the dominant side: < median and ≥ median
- Past treatment for ET (Yes, No)
- Response to past treatment for ET: Yes (Intermediate, Worked Well), No (No, a little), NA

If any of the subcategories has <5 patients fall into that category, the category will be combined with the next adjacent category with smaller counts. For example, if the number of patients falling into BMI category <18.5 kg/m² is <5, this category will be combined with the 18.5 to <25 kg/m² group. In the case of a variable of interest having only 2 subcategories and one of those subcategories has <5 patients, the variable will not be part of the sub-group analysis.

Forest plots for subgroup analysis for the primary endpoint at Day 91 – LS mean differences and associated confidence intervals – will be provided.

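### The rule for merging sparse subgroups is not limited to ordered variables, so in the two Yes/No/NA subgroups it can pool NA with a response group or erase the Yes/No contrast

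*SAP*

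**What the plan says.** SAP Section 8.3.3.4 lists the subgroups for the descriptive summary and MMRM of the primary endpoint, then gives one rule for small categories. The trigger is general: "If any of the subcategories has <5 patients fall into that category". The target is also general: "the category will be combined with the next adjacent category with smaller counts". The worked example is the lowest BMI class: "this category will be combined with the 18.5 to <25 kg/m² group". There is one exception. A variable with only two categories, one of them below 5 patients, is left out of the subgroup analysis.

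Three listed variables with more than two categories are not ordered as a whole:

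- "Alcohol helps tremor: Yes (Intermediate, Worked Well), No (No, a little), NA"
- "Response to past treatment for ET: Yes (Intermediate, Worked Well), No (No, a little), NA"
- "Race: White, Black or African American, Asian, Other"

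Nothing in the section limits merging to ordered variables, treats NA separately or says who falls into NA. No other section of the protocol or SAP does so. The results go into a Day 91 forest plot, and SAP Section 8.3.4 repeats the subgroup analyses for the ADL composite. SAP Section 6.1 gives the alcohol subgroup a specific purpose: after the amendment that permitted alcohol, the primary analysis is to be "repeated for categories of whether alcohol historically helped tremor".

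**The concern.** For BMI, age at diagnosis or onset, and years with ET, adjacent has a natural meaning: a merged class is a wider interval on the same scale. NA is not a point on the scale of benefit from alcohol or response to treatment, so its neighbour is simply whichever category is printed next to it. Applied as written, the rule can put participants with no response classification into a response row. It can also join Yes to No and leave NA as the only comparator, although the variable is there to compare Yes with No.

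At stake is the reading of a few forest-plot rows for the primary endpoint and the ADL composite. If programmers notice the problem and regroup sensibly, the grouping is no longer the prespecified one.

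**Working it through.** The plan states no figure on this point, so the check applies the rule and then asks how often it would act and how far one merge could change a row.

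**1. Merges that the rule allows for Yes, No, NA.** The phrase about smaller counts is read as choosing between two neighbours.

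| Sparse category | Neighbours | Result |
|---|---|---|
| NA | No only | NA participants enter the No row |
| Yes | No only | Yes and No pooled; only NA left to compare |
| No | Yes and NA | Joins the smaller: contrast lost if Yes, mixed row if NA |

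The two-category exception does not apply, because NA counts as a third category.

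**2. How often the rule would act.** Inputs: 104 planned monotherapy participants, up to 56 adjunct and 160 overall (SAP Section 5.2). The 104 reproduces: 22/0.85 = 25.9, so 26 per group, and 4 × 26 = 104. SAP Section 8.3.3 calls for analysis of the primary variable in all three populations. That the subgroup displays follow the same split is an assumption. The category shares p are also assumptions, since the documents give none.

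An empty category needs no merge, so the relevant probability is

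P(1 to 4 members) = P(X ≤ 4) − (1 − p)^N, with X binomial(N, p).

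Example, N = 104 and p = 0.02: 0.942 − 0.98^104 = 0.942 − 0.122 = 0.82.

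| Assumed share | N = 104 | N = 56 | N = 160 |
|---|---|---|---|
| 2% | 0.82 | 0.67 | 0.74 |
| 3% | 0.75 | 0.79 | 0.47 |
| 4% | 0.58 | 0.83 | 0.23 |
| 5% | 0.40 | 0.80 | 0.09 |
| 8% | 0.07 | 0.52 | 0.003 |
| 10% | 0.02 | 0.33 | <0.001 |

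The rule is likely to act on a category holding a few percent of participants. In the monotherapy cohort it is unlikely to act on one holding 8% or more.

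**3. How far one merge can move a row.** At most 4 patients join a host category of m patients, so they form at most 4/(m + 4) of the merged row: 4/9 = 44% for m = 5, 4/24 = 17% for m = 20, and 4/54 = 7% for m = 50.

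**4. Race.** In the order of Section 8.3.3.4, a sparse Black or African American group joins the smaller of White and Asian, a sparse Asian group joins the smaller of Black or African American and Other, and a sparse Other group joins Asian. Suppose the counts are Black or African American 3, Asian 2, Other 1 and White 104 − 6 = 98. The three small groups then pool with each other, and the result is White versus the rest.

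**The case against.** The strongest reply is that little is lost in practice, and much of it stands.

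- Merging is conditional. A reader might infer that No is routinely pooled with NA. The documents do not support that: the rule acts only below 5 patients, and no counts are given.
- Yes and No are built from graded answers (no, a little, intermediate, worked well), so they are neighbours on a real scale. Only NA lies outside it. That is correct, but pooling Yes with No still leaves a comparison with NA alone.
- With at most 4 Yes patients over four arms, there is no usable contrast to lose, and the fix also gives no estimate for that variable. This stands. The gain is that an ill-defined row is not printed.
- With a large host row, adding up to 4 patients hardly changes the estimate, and the fault is mainly one of labelling. The unmerged categories are summarised under SAP Section 8.2.4, and disease history is listed, so a careful reader could see the composition.
- A reader might infer that the race rows are arbitrary because SAP Section 8.2.3 uses another order, "Race (Black or African American, White, Asian, Other". That section governs baseline summaries and contains no merge rule. Under the order in Section 8.3.3.4, if White is the largest group (an assumption), the smaller-count clause usually pools small groups together, which can be interpreted. What remains is that the pooled category is not named in advance.

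The reply does not remove the textual gap. The SAP drops a two-category variable rather than merge it. Yes/No/NA is in substance a two-category variable with an extra group, yet the NA label takes it outside that exception.

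**Conclusion.** The point holds as a minor, conditional defect. Under SAP Section 8.3.3.4 as written, a sparse category in either Yes/No/NA variable leads to a row that mixes NA participants with a response group or to loss of the Yes/No contrast. No other text prevents this.

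The size depends on category shares that the documents do not give. Over assumed shares of 2% to 10%, the chance of 1 to 4 members runs from 0.82 to 0.02 in the monotherapy cohort. It is higher in the adjunct cohort at shares of 3% and above, but the SAP treats that cohort as exploratory. One merge moves at most 4 patients.

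A reader might go further and call all merged rows meaningless, or doubt the main result. Neither is supported. The most serious case is the lost Yes/No contrast; elsewhere the effect ranges from a diluted row to a mislabelled one. The primary MCP-Mod test, its alpha and its power do not depend on any subgroup row, and the SAP already treats the pairwise p-values as nominal. How small a category may be before the planned model is fitted is a separate question.

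**What to change.** Amend the small-category paragraph of SAP Section 8.3.3.4 as follows:

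- Limit merging by adjacency to ordered variables: BMI, age at ET diagnosis, age at onset, and the two years-with-ET variables.
- For alcohol response and response to past treatment, never pool NA with Yes or No. Report NA descriptively only. If Yes or No has fewer than 5 patients, omit the variable from the subgroup analysis, as the SAP already does for two-category variables.
- For race, name the pooled category in advance so that it does not depend on list position. Combining sparse groups into Other is one convention among several; what matters is that it is stated.

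The cost is a few sentences, with no new data and no change to the primary or secondary test. The one downside is that an occasional sparse variable gets no forest-plot row.

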8.3.4. Analysis of Secondary Efficacy Variables

Summarization and analysis of the secondary efficacy variables will be performed for the monotherapy cohort (main analysis), adjunct therapy cohort (for directional investigation, excluding MCP-Mod analysis), and overall.

The primary, sensitivity, supportive, and subgroup analyses performed for the primary endpoint will be repeated for the secondary endpoint, change from baseline in TETRAS ADL composite score.

8.4. Safety Analysis

Safety and tolerability of SAGE-324 will be evaluated by stratum (monotherapy cohort and adjunct therapy cohort) and overall using incidence of TEAEs, vital signs, 12-lead ECGs, clinical laboratory evaluations. Safety data will be listed by participant and summarized for each treatment group and SAGE-324 overall.

For safety summary tables, apart from adverse events, the choice of visit records for summarization at a given visit will be following the same rules as described in Section 8.3.2. Additional visit window schedules required for 12-lead ECG and laboratory data (chemistry, hematology, urinalysis, coagulation) appear in Table 6 and Table 7.

Table 0. Visit W	Indows for 12-lead ECG	
Scheduled Visit	Study Day of Expected Visit	Study Day Window for Visit
Day 1	Day 1	Day ≤1
Day 29 (±1 day)	29	Days 2 to 60
Day 91 (+1 day)	91	Days 61 to 96
Day 104 (+3 days)	104	>Day 97 (> last dose + 6 days)

Table 6:	Visit Windows	for 12-lead ECG

Note: Parenthesized study days and study day window is for unscheduled, EOT, and ET visits. For participants who have discontinued treatment prematurely with either unscheduled, EOT, or ET visits on or after 6 days of the last dose, those visits should be mapped to Day 104 using the parenthesized visit window listed (ie, visit date – last dose date >1).

Scheduled Visit	Study Day of Expected Visit	Study Day Window for Visit
Screening	Day -1	Days -28 to Day -1
Day 1 Predose	Day 1 Predose	Day 1 Predose
Day 8 (±1 day)	8	Day 1 Postdose to Day 11
Day 15 (±1 day)	15	Days 12 to 22
Day 29 (±1 day)	29	Days 23 to 36
Day 43 (±1 day)	43	Days 37 to 50
Day 57 (±3 days)	57	Days 51 to 64
Day 71 (±3 days)	71	Days 64 to 81
Day 91 (+1 day)	91	Days 82 to 96
Day 104 (±3 days)	104	\geq Day 97 (\geq last dose + 6 days

Table 7:Visit Windows for Laboratory Data (Chemistry, Hematology, Urinalysis,
Coagulation)

Note: Parenthesized study days and study day window is for unscheduled, EOT, and ET visits. For participants who have discontinued treatment prematurely with either unscheduled, EOT, or ET visits on or after 6 days of the last dose, those visits should be mapped to Day 104 using the parenthesized visit window listed (ie, visit date – last dose date >1).

All safety summaries will be prepared using the Safety Analysis Set and treatment received. See Table 8 for details on how safety endpoints will be presented. No statistical hypothesis testing will be conducted on the safety data.

Incidence	Raw Value	Change from Baseline	Clinical Significance	Abnormality	Derived PCS values
X	*				
	X, *	X			X, *
	X, *	Х	X, *	X, *	X (QTcF only)
	X, *	Х	X, *	X, *	Х
	Incidence X	Incidence Raw Value X * X, * X, * X, * X, * X, * X, *	IncidenceChange from BaselineX*X*XX,*X,*XX,*XX,*XX,*X	IncidenceRaw ValueChange from BaselineClinical SignificanceX*-XXXX,*XX,*XX,*X, *X,*X, *X,*X, *	IncidenceChange from BaselineClinical SignificanceAbnormalityX*X*XXX-XX,*X-X,*XX,*X,*X,*XX,*X,*X,*X,*X,*X,*X,*X,*X,*X,*

 Table 8: Presentation of Safety Endpoints

X = Safety Assessment will be summarized in tables

* = Safety Assessment will be presented in individual participant data listings

Note: Clinical significance and abnormality are based on Investigator review and collected directly from the eCRF.

Note: PCS = Potentially Clinically Significant.

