5. STUDY DESIGN

5.1. Overall Design

This study is a Phase 2, randomized, double-blind, placebo-controlled, dose-ranging study to evaluate the efficacy, safety, and tolerability of SAGE-324 in participants with ET. Participants, site staff, and sponsor personnel will be blinded to treatment allocations. This study includes a Screening Period of up to 28 days, a 90-day double-blind Treatment Period (90 days of dosing), and a 14-day Follow-up Period. See the Schedule of Assessments (Appendix A) for the full list of study assessments and timings. A schematic of the study is presented in Figure 1.

Participants who have provided informed consent will undergo screening assessments to determine eligibility. The Screening Period may be extended for an additional 14 days (to a total of 42 days) for subjects requiring additional time to taper ET medication (other than propranolol), after approval from the sponsor.

Following completion of screening and Day 1 eligibility assessments, participants will be randomly assigned to 1 of 4 treatment groups (placebo or SAGE-324: 15 mg, 30 mg, or 60 mg, oral daily) in a 1:1:1:1 ratio, stratified by baseline propranolol use (adjunct therapy).

The 15-mg dose group will receive 15 mg of SAGE-324 from Day 1 to Day 90.

The 30-mg dose group will receive 30 mg of SAGE-324 from Day 1 to Day 90.

The 60-mg dose group will receive 15 mg of SAGE-324 from Day 1 to Day 14, then 30 mg from Day 15 to Day 28, then 45 mg from Day 29 to Day 42, and then 60 mg from Day 43 to Day 90.

Starting on Day 1, after randomization, participants will receive a single dose of IP once daily for 90 days on an outpatient basis, to be taken before bed, with a snack if bedtime is not within 2 hours of the evening meal. During the Treatment Period, participants will return to the study center for efficacy and safety assessments as specified in Appendix A.

Follow-up visits will be conducted on an outpatient basis on Days 97 and 104. Participants will continue to complete questionnaires as indicated in Appendix A and will return to the clinic approximately 6 days after the last dose of IP (ie, Day 97) for efficacy and safety monitoring. Participants will return to the study center for an End of Study (EOS) visit approximately 13 days following the last dose of IP (ie, Day 104); the EOS visit will be conducted at the time of discontinuation if this occurs any time before Day 104.

No dose reductions of SAGE-324 will be permitted.

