8.3.2. Visit Windows for Efficacy Analyses

The scheduled visits will not be windowed and will be used at nominal visit value for treatment and follow-up period visits (Day 1, Day 8, Day 15, Day 29, Day 43, Day 57, Day 71, Day 91, Day 97, Day 104). Unscheduled, end-of-treatment (EOT), and early termination visits (ETV) that happen on or before one day after the last dose will be mapped to a scheduled visit for analysis using the date of collection/assessment and Day 1, first dose date, as a basis to determine study day and then study day will be mapped to the intended visit according to the visit windows specified in the Table 2. Unscheduled, EOT, or ET visits that happen on or after 1 day after the last dose will be windowed using relative days since last dose date; the mapping will follow the visit window in Table 2. To accommodate as much data as possible into analysis, these windows have been widened relative to protocol-specified operational windows to have no gap between them; these windows are used for analysis purposes only.

Scheduled Visit	Study Day of Expected Visit	Study Day Window for Visit
Screening	Day -1	Days -28 to Day -1
Day 1 Predose	Day 1 Predose	Day 1 Predose
Day 8 (±1 day)	8	Day 1 Postdose to Day 11
Day 15 (±1 day)	15	Days 12 to 22
Day 29 (±1 day)	29	Days 23 to 36

Table 2:	Visit	Windows	for	Efficacy	Analy	vsis
				•		

Scheduled Visit	Study Day of Expected Visit	Study Day Window for Visit
Day 43 (±1 day)	43	Days 37 to 50
Day 57 (±3 days)	57	Days 51 to 64
Day 71 (±3 days)	71	Days 65 to 81
Day 91 (+1 day)	91	Days 82 to 96
Day 97/last dose +7 days (±3 days) 97/last dose+ 7 days		Days 97 to 100 (last dose+6 days, last dose + 10 days)
Day 104/last dose + 14 days $(\pm 3 \text{ days})(*)$	104/last dose + 14 days	≥ Day 101 (last dose + 11 days, last dose + 17 days)

Note: Parenthesized study days and study day windows are for unscheduled, EOT, and ET visits. For participants who have discontinued treatment prematurely with either unscheduled, EOT, or ET visits on or after 6 days of the last dose, those visits should be mapped to Day 97 or Day 104 using the parenthesized visit windows listed (ie, visit date – last dose date >1).

Note: (*) The scheduled visit of Day 104/last dose visit is for efficacy analysis excluding TETRAS.

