Once analysis visits are assigned based on the visit windows, all visits, including scheduled visits, unscheduled visits, and EOT/ETV visits, will be eligible for being flagged as the "analyzed record" within the analysis visit window; a participant's individual analysis visit window could potentially contain more than 1 visit. In the event of multiple visits falling within an analysis window or in case of a tie relative to number of days from the scheduled study day, the following rules will be used in sequence to determine the "analyzed record" for the analysis visit window:

- If data from the scheduled visit is available within treatment period, then the scheduled visit data will be used.
- If no data from the scheduled visit within treatment period is available, then the windowed visit data will be used.
- If more than one visit is in the same target day window, the data closest to the target day will be used.
 - If there is a tie with distance from visits to target day, the visit after the the target day will be used.

The summary by visit will use the "analyzed records" only – at most one per participant per visit. The data not flagged as the "analyzed record" will be included in listings. An unscheduled visit that does not fall under any analysis window (e.g. in case one is available after Day 107) will remain in the database and will be included in the listings.

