8.4.3. Electrocardiogram

The average of multiple values collected at one visit will be used for summarization, including baseline ECG values. For each ECG measurement (heart rate and PR, QRS, QT, and QTcF intervals), the observed value at each scheduled visit and change from baseline at each scheduled visit will be provided by treatment group. This summary will also include last values on treatment and on study. Last value on treatment is defined as the last post-baseline value between first dose of IP (exclusive) and up to last dose of IP + 1 days (inclusive). Last value on study is defined as the last post-baseline value after the first dose of IP.

In addition, the number and percentage of participants with PCS and potentially clinically significant change (PCSC) values will be summarized by visit/timepoint and for any time post-baseline. Potentially clinically significant values will be identified for ECG parameters as outlined in Table 13.

A shift table of overall ECG interpretation from baseline to scheduled post-baseline visits will be presented for the following categories: 'Normal', 'Abnormal, Not Clinically Significant', and 'Abnormal, Clinically Significant'. The shift table will be presented by visit and treatment group.

Clinically significant abnormal findings will be reported as adverse events. The average of the multiple values collected at one visit of each parameter will be listed by participant.

Units	Criteria for PCS Values (Observed Values)		Criteria for PCSC Values (Change from Baseline)	
	High	Low	Increase	Decrease
msec	 >450 msec and ≤480msec >480 msec and ≤500msec >500 msec 	NA	>30 msec and ≤60 msec >60 msec	NA

 Table 13: Potentially Clinically Significant Values for QTcF

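### The ECG interpretation shift table is by visit only, so for 60-mg participants who stop treatment by about Day 60 it can omit the on-treatment ECG taken at their highest dose

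*SAP*

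**What the plan says.** Post-baseline ECGs are scheduled on Day 29, Day 91/EOT and Day 104 only (protocol Table 2; SAP Appendix A). For safety tables other than adverse events, SAP Section 8.4 states that "the choice of visit records for summarization at a given visit will be following the same rules as described in" Section 8.3.2, and Table 6 supplies the ECG windows: "Day 29 (±1 day) 29 Days 2 to 60", then Days 61 to 96 for Day 91.

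Section 8.3.2 treats two kinds of record differently:

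- Scheduled visits: "The scheduled visits will not be windowed and will be used at nominal visit value for treatment and follow-up period visits".
- Unscheduled, EOT and ETV visits "that happen on or before one day after the last dose will be mapped to a scheduled visit for analysis" by study day. Later ones "will be windowed using relative days since last dose date".

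Where several records share a slot, the first rule is "If data from the scheduled visit is available within treatment period, then the scheduled visit data will be used". A by-visit summary uses no more than one record per participant per visit.

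In the 60-mg arm, Section 5.1 gives 15 mg to Day 14, 30 mg to Day 28, "then 45 mg from Day 29 to Day 42, and then 60 mg from Day 43 to Day 90". The 15-mg and 30-mg arms stay on one dose throughout. Doses are taken at bedtime.

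Section 8.4.3 plans three ECG summaries. The numeric one adds last-on-treatment (up to one day after the last dose) and last-on-study rows to the visit rows. The QTcF threshold counts are given by visit and for any time after baseline. For the overall interpretation, "The shift table will be presented by visit and treatment group", with no further row.

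**The concern.** All arms share one ECG calendar, but only the 60-mg arm changes dose inside the Table 6 Day 29 window. That window covers all four of the arm's dose levels. For someone who stops during it, the record kept and the record set aside can come from different doses, and the kept one is the lower. In the 15-mg and 30-mg arms both records come from the same dose, so those arms may lose a later record but never a dose level.

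At stake is the comparison of ECG interpretation between dose groups. Section 8.4.3 gives two of its three ECG summaries a route around the visit windows. The shift table has none, so its 60-mg column can omit on-dose ECGs of participants who stopped early.

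The issue is specific to ECGs. Laboratory tests also have scheduled visits on Days 43, 57 and 71, with matching windows in Table 7.

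**Working it through.** **1. The plan's own cut.** Day 60 is the midpoint of the adjacent scheduled ECGs: (29 + 91)/2 = 60. The same rule reproduces the upper limits in SAP Table 2: (8 + 15)/2 = 11.5, giving 11; (15 + 29)/2 = 22; (29 + 43)/2 = 36; (43 + 57)/2 = 50; (57 + 71)/2 = 64; (71 + 91)/2 = 81. The limit is a consistent convention, not a slip.

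**2. Dose behind the scheduled Day 29 ECG.** With bedtime dosing, a clinic ECG on Day 28 or 29 follows a 30-mg dose. One done on Day 30, which the ±1-day tolerance allows, could by the calendar follow the first 45-mg dose. Hence 'normally' 30 mg.

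**3. Dose behind the EOT ECG, taken one day after the last dose (60-mg arm).**

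| Last dose | ECG day | Dose before ECG | Table 6 slot | In visit rows if a scheduled Day 29 ECG exists? |
|---|---|---|---|---|
| Days 29–42 (14 days) | 30–43 | 45 mg | Day 29 | No |
| Days 43–59 (17 days) | 44–60 | 60 mg | Day 29 | No |
| Days 60–89 (30 days) | 61–90 | 60 mg | Day 91 | Yes |

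**4. The one-day boundary.** At exactly one day after the last dose, both mapping sentences in Section 8.3.2 apply as written. The note under Table 6 describes the relative-day mapping as being for a difference greater than 1, which points to study-day mapping at one day. Under the other reading the ECG has no Table 6 window. In both cases it is missing from the visit rows.

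**5. Where the ECG does appear.** An ECG zero or one day after the last dose meets the last-on-treatment definition in Section 8.4.3, so heart rate, PR, QRS, QT and QTcF are all recovered in the numeric summary. It also enters the any-time QTcF counts. It does not enter the shift table.

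**6. Size.** Assumptions: each EOT ECG falls one day after the last dose, a scheduled Day 29 ECG exists, and early stops are spread evenly over last-dose Days 1 to 89. The arm has 26 + 14 = 40 participants (monotherapy plus adjunct).

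- Share of full-dose early stoppers (last dose Days 43 to 89, 47 days): 17/47 = 36%.
- Share of all early stoppers: 17/89 = 19%.
- Expected number losing a 60-mg ECG = 40 × stopping rate × 17/89. At 15% this is 1.1; at 30%, 2.3; at 40%, 3.1.
- The 45-mg case adds 40 × stopping rate × 14/89: 0.9 at 15% and 2.5 at 40%.

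The 15% is the plan's nonevaluable rate, used as a stand-in. The documents give no stopping rate, and 30% and 40% only show the range.

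**The case against.** The strongest reply is that the SAP already covers most of this. The last-on-treatment row captures exactly the zero-to-one-day lag on which the problem depends, for every ECG interval. No QTcF threshold event is lost from the any-time counts, and ECG threshold criteria exist only for QTcF. Clinically significant findings are reported as adverse events, all ECGs are listed, and no hypothesis test is run on safety data. All of that stands. What remains is the visit-specific rows and one descriptive shift table, where movements to abnormal but not clinically significant have no summary other than the visit rows.

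The counts can also fairly be called near an upper bound. Protocol Section 8.4.1 only encourages participants who stop to attend the EOT visit and sets no interval. An ECG two to about six days after the last dose has no clear Table 6 window, and later ones go to Day 104. Without a scheduled Day 29 ECG, the later ECG is itself shown in that slot.

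A reader might infer more than the documents support:

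- *That Table 6 relabels every ECG up to Day 60.* It does not. Scheduled ECGs keep their nominal visit, and ECGs well after the last dose go to Day 104.
- *That the Day 60 limit is wrong and should move to the last titration step.* It follows the midpoint rule used elsewhere. A cut after Day 43 would label a Day 44 ECG, 15 days from Day 29 and 47 from Day 91, as Day 91. It would also leave the 45-mg case untouched.
- *That the omitted participants are those most likely to show an ECG effect.* The documents do not say so. The common events they describe are somnolence, dizziness and feeling of relaxation.

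**Conclusion.** The point holds as a gap in one table, not as a fault in Table 6. Under the stated rules, a 60-mg participant with a last dose on Days 43 to 59, an EOT, ETV or unscheduled ECG the next day and a scheduled Day 29 ECG is represented in the interpretation shift table by an ECG normally taken at 30 mg. The 60-mg ECG is absent. Last doses on Days 29 to 42 lose a 45-mg ECG likewise.

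The day ranges follow directly from the SAP for an ECG one day after the last dose. The estimate of about 1 to 3 of 40 rests on the assumptions in the working and is more likely too high than too low at a given stopping rate. Nothing here affects efficacy, the numeric last-on-treatment summary or the any-time QTcF counts. It is a minor improvement, worth making because the same section already does it for the other two ECG summaries.

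**What to change.** In SAP Section 8.4.3 and display Table 14.3.4.5.2, add two entries to the ECG interpretation shift table beside the scheduled visits:

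1. Last value on treatment, using the definition already in Section 8.4.3.
2. Worst value at any time post-baseline, including EOT, ETV and unscheduled ECGs, ordered normal, abnormal not clinically significant, abnormal clinically significant.

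Leave the Table 6 limits unchanged. The last-on-treatment entry works under either reading of the one-day boundary and captures both the 45-mg and the 60-mg ECGs. The worst-value entry does not depend on the lag after the last dose.

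The cost is a sentence in the SAP and extra rows or columns in one table. No visits, ECGs or data are added. If the change comes after database lock, Section 2 of the SAP requires it to be documented in the clinical study report.
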